APPENDIX E: Dermatology Life Quality Index (DLQI)

The aim of this questionnaire is to measure how much your skin problem has affected your life OVER THE LAST WEEK. Please check one box for each question.

1.	Over the last week, how itchy, sore, painful or stinging has your skin been?	Very much 	A lot 	A little 	Not at all 	
2.	Over the last week, how embarrassed or self conscious have you been because of your skin?	Very much 	A lot 	A little 	Not at all 	
3.	Over the last week, how much has your skin interfered with you going shopping or looking after your home or yard ?	Very much 	A lot 	A little 	Not at all 	Not relevant 
4.	Over the last week, how much has your skin influenced the clothes you wear?	Very much 	A lot 	A little 	Not at all 	Not relevant 
5.	Over the last week, how much has your skin affected any social or leisure activities?	Very much 	A lot 	A little 	Not at all 	Not relevant 
6.	Over the last week, how much has your skin made it difficult for you to do any sport ?	Very much 	A lot 	A little 	Not at all 	Not relevant 

7.	Over the last week, has your skin prevented you from working or studying ?	yes		Not relevant 
		no		
8.	Over the last week, how much has your skin been a problem at work or studying ?	A lot		Not relevant 
		A little		
		Not at all		
		Very much		
9.	Over the last week, how much has your skin caused any sexual difficulties ?	A lot		Not relevant 
		A little		
		Not at all		
		Very much		
10.	Over the last week, how much of a problem has the treatment for your skin been, for example by making your home messy, or by taking up time?	A lot		Not relevant 
		A little		
		Not at all		
		Very much		

Please check you have answered EVERY question. Thank you.

APPENDIX F: Health Assessment Questionnaire modified for Spondyloarthropathies (HAQ-S)

HEALTH ASSESSMENT QUESTIONNAIRE MODIFIED FOR THE SPONDYLOARTHROPATHIES (HAQ-S) 1 OF 3

Modified Health Assessment Questionnaire for Spondyloarthropathies (HAQ-S)

Place an "x" in the box which best describes your abilities OVER THE PAST WEEK:

	WITHOUT ANY DIFFICULTY	WITH SOME DIFFICULTY	WITH MUCH DIFFICULTY	UNABLE TO DO
--	---------------------------	-------------------------	-------------------------	-----------------

DRESSING AND GROOMING

Are you able to:

Dress yourself, including shoelaces and buttons?	 0	 1	 2	 3
Shampoo your hair?	 0	 1	 2	 3

ARISING

Are you able to:

Stand up from a straight chair?	 0	 1	 2	 3
Get in and out of bed?	 0	 1	 2	 3

EATING

Are you able to:

Cut your own meat?	 0	 1	 2	 3
Lift a full cup or glass to your mouth?	 0	 1	 2	 3
Open a new milk carton?	 0	 1	 2	 3

WALKING

Are you able to:

Walk outdoors on a flat ground?	 0	 1	 2	 3
Climb up five steps?	 0	 1	 2	 3

Please check any AIDS OR DEVICES that you usually use for any of the above activities:

 Devices used for dressing (button hook, zipper pull etc.)	 Built up or special utensils	 Crutches
 Special or built up chair	 Cane	 Wheelchair
 Walker		

Adalimumab
P13-990
FINAL 06 December 2012

Are y

Daltry L
J Rheum

Adalimumab
P13-990
FINAL 06 December 2012

APPENDIX G: Study Plan

	Screening	Baseline	Month 3	Month 6	Month 12	Month 18 (or term.)
Informed Consent	♦					
Inclusion/ Exclusion Criteria	♦					
Medical History		♦				
Demographics (gender, year of birth, race)		♦				
AS & PSA diagnosis		♦				
Previous and current AS&PsA treatments		♦				
Extra articular disease manifestations		♦	♦	♦	♦	♦
Educational background		♦				
Employment situation		♦	♦	♦	♦	♦
Disease activity measures and clinical evaluations : DAS28*, BSA*, physician assessment disease activity, acute phase reactants (CRP/ESR), BASDAI**, patient assessment of disease activity, patient assessment of pain						
		♦	♦	♦	♦	♦
Healt related quality of life (DLQI*, HAQ-DI*, HAQ-S**)		♦	♦	♦	♦	♦
WPAI-SHP		♦	♦	♦	♦	♦
Serious Adverse Events		♦	♦	♦	♦	♦

Screening and basline assessments can happen in the same visit

Follow up visits are according to daily clinicla practice, no additional visits are planned for the study only.

*only completed for PsA patients

** only completed for AS patients

1. METHODOLOGY

The purpose of this statistical analysis plan is to provide detailed information on the statistical analysis of the data of study P13-990. The plan is based on the final protocol, incorporating administrative change 1, dated 17 December 2015.

1.1 *Introduction*

Ankylosing spondylitis (AS) and psoriatic arthritis (PsA) are both associated with often debilitating clinical symptoms, reduced functional impairment and significant impact on quality of life. As a consequence both diseases imply a significant economic burden, arising from both the direct costs of medical and disability. Health economics data becomes increasingly important to justify the costs of medicines.

Very limited data are available about the employment status and the work productivity of patients with AS and PsA in Belgium. The same is true for the impact of adalimumab treatment on employment status and work productivity.

The aim of this study is to analyse the employment status and work productivity of patients with AS and PsA before and after the start of adalimumab and to look at the relationship between employment status, work productivity, disease activity and clinical evaluations.

1.2 *Study Objectives and Endpoints*

1.2.1 *Study Objectives*

The main objective of the study is to observe in daily practice the evolution of work productivity over 18 months in AS and PsA patients after the start of adalimumab treatment.

The following questions were addressed:

- What is the employment status of AS and PsA patients with active disease before initiation of adalimumab?
- In the patients who work at baseline, what is their work productivity?
- Does adalimumab therapy enable people with AS and PsA to return to work or work more productively?

The secondary objectives are to:

- Investigate if there is a difference in evolution of employment status and work productivity after initiation of adalimumab treatment between AS and PsA patients throughout the study
- Investigate the relationship between disease activity and employment situation and the relationship between clinical evaluations and employment situation at baseline and after 18 months
- Investigate possible correlations between disease activity and work productivity and between clinical evaluations and work productivity

1.2.2 *Study Endpoints*

The primary endpoints is Total Work Productivity Impairment (TWPI) due to AS/PsA:

18 months versus baseline in all patients, measured by the WPAI-SHP questionnaire.
(patient reported outcome)

The secondary endpoints are:

- Total Work Productivity Impairment (TWPI) due to AS and PsA separately: 18 months versus baseline in all patients, measured by WPAI-SHP questionnaire.
(patient reported outcome)
- Evolution over time of (observed for AS and PsA combined and separately) :
 - Number of patients that are employed at each assessed visit
 - Percentage of missed working hours (absenteeism) due to As/PsA 7 days prior to each visit
 - Assessment of the effect of As/PsA on the ability to do regular daily activities during the 7 days prior to each visit (activity impairment)
 - Assessment of the effect of As/PsA on productivity while working during the 7 days prior to each visit (presenteeism)
- Health Related Quality of Life (Patient reported outcome)
 - HAQ-DI (PsA)
 - DLQI (PsA)
 - HAQ-S (AS)
- Disease activity measures and clinical evaluations:
 - DAS28 (PsA)
 - BSA (PsA)
 - BASDAI (AS)
 - Acute phase reactants (CRP / ESR)
 - Physician assessment of disease activity by means of a visual analogue scale (VAS)
 - Patient assessment of disease activity (VAS)
 - Patient assessment of pain (VAS)

1.3 Study Design

The study population consists of adult patients between 18 and 50 years of age, with diagnosed AS / PsA in whom adalimumab treatment was initiated. All medications were prescribed in the usual manner in accordance with the terms of the marketing authorization and in line with the Belgian reimbursement criteria.

The patients provided written informed consent and gave written authorization to the investigator to use and/or disclose personal and/or health data before entry into this observational study.

200 patients were to be enrolled in 20 investigational sites in Belgium during a recruitment period of 12 months. Centers could be University hospitals, regional hospitals, or private practices, with Experience in AS / PsA patient care. Other criteria to be used when selecting investigators were experience and interest to participate in observational studies, sufficient patient potential to include the required number of patients, required availability and resources to participate, and acceptance of the study protocol and study procedures.

Patient data were collected during routine visits at baseline and afterwards preferentially after 3, 6, 12, and 18 months. The total duration of the observation period for the study was therefore approximately 18 months.

This is a local, post marketing, observational study (PMOS). As this is an observational study, no additional visits were required, no study specific medication was provided and no other interventional procedures additional to those comprising routine clinical practice were performed.

All of the following criteria were to be fulfilled to make the patient eligible for the study:

- Inclusion criteria:
 - Age \geq 18 and \leq 50 years
 - Patient diagnosed with AS or PsA
 - Patient newly initiated on adalimumab (according to the Marketing Authorization and Belgian reimbursement criteria)
 - Patient has signed the Informed Consent Form.
- Exclusion criteria:
 - Patients having any of the contraindications mentioned in the SmPC
 - Patients previously treated with biologics
 - Patients participating in other AbbVie-sponsored trials.

A patient was withdrawn from the study if he/she withdrew consent or if the investigator found it no longer appropriate to keep the patient in the study.

1.4 Sample Size Justification

The main objective of this study is to observe the working status in AS and PsA patients before and after the start of adalimumab therapy in daily practice. The primary variable is the change in total work productivity impairment (TWPI) due to AS/PsA between baseline and Month 18. The change will be evaluated in a descriptive way by means of the mean change observed in the study and its 95% confidence interval.

The number of patients to be enrolled (200) was determined on the basis of the recruiting capacity of the participating investigational sites during the foreseen recruitment period of 12 months.

Based on data from Reilly et al¹ it is estimated that about 65% of the patients of the study population are working and therefore evaluable for work productivity impairment.

Supposing that 80% of the employed patients have data available over an 18 month period, the mean change in TWPI will be estimated on the basis of data for about 100 patients.

Based on data for a 16 week treatment period it is estimated that the standard deviation of the change in TWPI will be about 23.8. Since the estimate to be made is for an 18 month treatment period, 95% confidence intervals are also calculated for a somewhat more important standard deviation, arbitrarily set equal to 30.0.

¹ Reilly MC, Zbrozek AS, Dukes EM. The validity and reproducibility of a work productivity and activity impairment instrument. *Pharmacoeconomics*. 1993; 4: 353–65.

The table below contains 95% confidence intervals on the mean change for some possible mean changes (-10.0, -15.0 and -20.0), and for standard deviations (SD) of 23.8 and 30.0, supposing data will be available for 100 patients:

Mean change	SD	95% CI
-10.0	23.8	[-14.7 ; -5.3]
-15.0	23.8	[-19.7 ; -10.3]
-20.0	23.8	[-24.7 ; -15.3]
-10.0	30.0	[-16.0 ; -4.0]
-15.0	30.0	[-21.0 ; -9.0]
-20.0	30.0	[-26.0 ; -14.0]

These intervals show that quite precise estimates can be obtained of the change in TWPI on the basis of the planned sample size.

1.5 Study Data Considered for the Analysis

The following data are used for the analysis:

Data only collected at screening (baseline)

- Date of inclusion (screening) and date informed consent form was signed
- Demographic data
 - Year of birth
 - Gender
 - Ethnic origin (Caucasian, Hispanic, Black, Asian, Other).
- Indication for adalimumab therapy (ankylosing spondylitis, psoriatic arthritis) and year of diagnosis.
- Extra-articular disease manifestations: None or
 - Psoriasis
 - Inflammatory bowel disease
 - Uveitis
For each manifestation: Yes/no and (currently active, currently inactive)
- Smoking status (never smoked, ex-smoker, smoker, unknown)
- Other medical history: None or
 - Cardiovascular diseases
 - Cardiovascular risk factors
 - Diabetes
 - Renal disease
 - Hepatic disease
 - Lung disease
 - Mental disorders
 - Other and specification
- Medication history
 - Analgesics
 - NSAIDs

- DMARDs
- Steroids
- Biologic therapy.
- Education background (highest level achieved): None, primary school, secondary school, higher education (non-university), university.
- Start date adalimumab therapy.

Data collected at each visit

- Date of visit
- Employment situation (to be answered at baseline, and at each follow-up visit in case of any change since the last visit):
 - Current employment status:
 - Housewife/houseman, due to As/PsA (yes, no)
 - Unemployed, due to As/PsA (yes, no)
 - Retired, due to As/PsA (yes, no)
 - Part-time employed: Percentage, due to As/PsA (yes, no)
 - Full-time employed
 - Student.
 - Current job content:
 - Professional or technical
 - Administrative or managerial
 - Sales
 - Service tasks
 - Agricultural
 - Production/manufacturing, transport equipment operator, laborer
 - Armed forces
 - Other and specification.
 - Current occupational situation:
 - Employee
 - Independent
 - Public/civil servant
 - Volunteer
 - Other
- Disease activity measures and clinical evaluations:
 - Only PsA
 - Body Surface Area (BSA) affected (no psoriatic lesions, <3%, 3-10%, 11-20%, >20%).
 - DAS28 score.
 - Only AS
 - BASDAI
 - Consists of 6 items assessed on ordinal scales. Higher scores indicate higher severity. The scores for Items 1 to 5 are integers between 0 and 10. The scores for Item 6 is a continuous assessment between 0 and 10.
 - The total score is calculated as:
[(Item 1+Item 2+Item 3+Item 4)+(Item 5+Item 6)/2]/5

PsA and AS

- Physician's global assessment of disease activity by means of a 100 mm VAS (0=no disease activity, 100=maximal disease activity).
- Patient's global assessment of disease activity by means of a 100 mm VAS (0=no disease activity, 100=maximal disease activity).
- Patient's global assessment of pain by means of a 100 mm VAS (0=no pain, 100=serious pain).
- Acute phase reactants:
 - o Recent ESR (mm/h)
 - o Recent CRP (mg/dl).
- Health-related Quality of Life (QOL):
 - Only PsA*
 - DLQI consisting of 10 questions.
 - o For all 10 questions except question 7 the answers are coded as 0=not at all, 1=a little, 2=a lot, 3=very much. The answer 'not relevant' (questions 3, 4, 5, 6, 8, 9, and 10), and an unanswered question are coded as 0.
 - o Question 7 consists of 2 parts:
 - An answer 'yes' to the first part is coded as 3 (very much).
 - In case of an answer 'no' or 'not relevant' to the first part or if the first part is unanswered the following codes are used for the answer to the second part: 0=not at all, 1=a little, 2=a lot.
 - In case the first part is answered 'no' or 'not relevant' or is unanswered, and the second part is unanswered the score is 0.
 - HAQ-DI consisting of 20 questions coded as 0=without any difficulty, 1=with some difficulty, 2=with much difficulty, 3=unable to do. The questions are divided into the following categories:
 - o Dressing and grooming: Questions 1, 2
 - o Arising: Questions 3, 4
 - o Eating: Questions 5, 6, 7
 - o Walking: Questions 8, 9
 - o Hygiene: Questions 10, 11, 12
 - o Reach: Questions 13, 14
 - o Grip: Questions 15, 16, 17
 - o Common daily activities: 18, 19, 20.

Only AS

- HAQ-S consists of 3 parts:
 - o 25 questions coded as 0=without any difficulty, 1=with some difficulty, 2=with much difficulty, 3=unable to do. The first 20 questions are almost identical with the 20 questions of the HAQ-DI questionnaire and divided into the same categories. Questions 21, 22, and 23 are regrouped into a separate (9th) category ('other daily activities'), and questions 24 and 25 belong to the additional (10th) category 'driving a car'. Furthermore, use of devices can be indicated (7 for categories 1 to 4, and 6 for categories 5 to 9), and the need of outside help can be indicated for 4 items (hygiene, reach, grip and opening, and errands and chores).
 - o 1 question assessed on a 5 point ordinal scale (entirely, usually, moderately, a bit, not at all), concerning the possibility of performing daily activities such as going for a walk, going up stairs, carrying errands, and moving a

chair.

- 3 additional items evaluating pain during the past week on a scale from 0 (no pain) to 100 (severe pain), general health on a scale from 0 (very good) to 100 (very bad), and stiffness on a VAS (with 0 mm=not stiff, 100 mm = very severe stiffness).

PsA and AS

- Work Productivity and Activity Impairment – Specific Health Problem (WPAI-SHP) questionnaire at baseline and each follow-up visit:
 - Q1: Do you presently have a professional activity? (yes, no).
 - In case the subject has a professional activity:
 - Q2: Number of hours work missed during the past 7 days due to the disease.
 - Q3: Number of hours work missed during the past 7 days due to other reasons.
 - Q4: Number of hours worked during the past 7 days.
 - Q5: In case the subject worked during the past 7 days (number of hours worked >0): To what extent did the disease decrease productivity?: 0=no effect, to 10=could not work at all.
 - Q6: To what extent did the disease decrease the capacity to perform usual daily activities?: 0=no effect, to 10=could not perform any daily activities.
- Adalimumab treatment recorded at each follow-up visit:
 - Was there any change in adalimumab treatment? (yes, no)
 - In case of change this was to be recorded in the adalimumab treatment section with for each treatment period: Type (pen or syringe), dose, frequency (EOW or other), start and stop date (or ongoing at end of study).
- Other AS/PsA treatment:
 - Drug name.
 - Dose and frequency.
 - Start date, and stop date or ongoing.
- Serious adverse events (SAEs):
 - Event description.
 - Final diagnosis.
 - Onset date.
 - End date if recovered.
 - Serious (yes, no), and if yes, criterion for seriousness (hospitalization, prolongation of hospitalization, persistent or significant disability or incapacity, life threatening, death and date, congenital anomaly, medically important event, elective abortion, miscarriage).
 - Causality with adalimumab (probable, possible, probably not related, not related, not assessable).
 - Action taken after the event (adalimumab dosage increased, adalimumab dosage decreased, none, adalimumab discontinuation).
 - Outcome (recovered, not recovered, recovering, improved, worsened, death, unknown, recovered with sequelae and specification).

Study termination

- Study completion or study withdrawal date.
- Reason for study termination:
 - Study completion
 - Withdrawal of consent.
 - Lost to follow-up.
 - Discontinued due to administrative reasons.
 - Death.
 - Serious adverse event.
 - Discontinued due to other reason.

1.6 Derived Variables

- Age (years) = year of inclusion – year of birth
- Study duration (month) =
$$12 \times (\text{date patient completed study/withdrew} - \text{date of inclusion}) / 365.25$$
- Adalimumab treatment duration (month) =
$$12 \times [\text{first of (last stop date adalimumab and date patient completed study/withdrew)} - \text{start date adalimumab} + 14] / 365.25$$
- BASDAI total score = [(Item 1+Item 2+Item 3+Item 4)+(Item 5+Item 6)/2]/5:
If one of items 5 or 6 is missing the other is considered.
If one of items 1, 2, 3, 4, or the average of 5 and 6 is missing, the missing item is estimated by the average of the available among items 1, 2, 3, 4, and the average of items 5 and 6. If more than one of these is missing, the total score is missing.
- BASDAI category (axial disease):
 - Yes: BASDAI total score >4
 - No: BASDAI total score ≤ 4 .
- HAQ-DI
Each of the 8 categories is given a score by taking the maximum score of all questions in the category (question in each category with the highest score is the score for that category).
The HAQ-DI will be calculated by dividing the sum of the category scores by the number of categories with at least 1 question answered. If fewer than 6 categories have responses, no disability score will be calculated. The HAQ-DI score ranges from 0 to 3. A lower HAQ-DI disability score indicates better function.
- HAQ-S
Each of the 10 category is given a score by taking the maximum score of all questions in the category (question in each category with the highest score is the score for that category). If the maximum score equals 0 or 1, but a device related to that category is used, or help from another person is provided for the category, then the category score is increased to 2. If the category score is already 2, and a device related to that category is used, or help from another person is provided for the category, the score for that category remains 2. The table below details how each aid and device is associated with the category scores.

If all questions within a given category are unanswered, no score will be provided for that category. The HAQ-S will be calculated by dividing the sum of the category scores by the number of categories with at least 1 question answered. If fewer than 6 categories have responses, no disability score will be calculated. The HAQ-S score ranges from 0 to 3. A lower HAQ-S disability score indicates better function.

NOTES:

- The assignment of aids and devices to categories is done as follows:

Aid or device	Associated with category
Cane, walker, crutches, wheelchair	Walking
Devices used for dressing	Dressing and grooming
Built up or special utensils	Eating
Special or built up chair	Arising
Raised toilet seat	Hygiene
Bath tub seat	Hygiene
Jar opener (for jars previously opened)	Grip
Bath tub bar	Hygiene
Long-handled appliances for reach	Reach
Long-handled appliances for bathroom	Hygiene

- No aids or devices are assigned to the category 'Activities'.
- Aids and devices specified in the 'Other' field will not be used in the calculations.
- Help from another person for errands and chores is assigned to the category 'Activities'.
- Help from another person for gripping and opening things is assigned to the category 'Grip'.
- WPAI Questionnaire:
 - Absenteeism = Percentage work time missed due to disease = $100 \times Q2 / (Q2+Q4)$
 - Presenteeism = Percentage impairment while working due to the disease = $100 \times Q5 / 10$
 - Total work productivity impairment (TWPI) due to disease = Absenteeism (%) + extent to which the disease decreased productivity (%) x [number of hours worked /(number of hours work missed due to the disease + number of hours worked)] = $100 \times Q2 / (Q2+Q4) + 100 \times [1 - Q2 / (Q2 + Q4)] \times [Q5 / 10]$
 - Percentage activity impairment due to disease = Extent to which the disease affected the ability to perform usual daily activities = $100 \times Q6 / 10$
- Dermatology Life Quality Index (DLQI) questionnaire
 - In case one question is unanswered it is given a score of 0. In case 2 or more questions are unanswered the DLQI score is not calculated. Question 7 is considered unanswered if both parts are unanswered.
 - The DLQI score is calculated as the sum of the scores of the individual questions.

- DLQI category
 - o 0-1: No effect
 - o 2-5: Small effect
 - o 6-10: Moderate effect
 - o 11-20: Very large effect
 - o 21-30: Extremely large effect.
- Regrouped DLQI category
 - o ≤ 5
 - o > 5
- DLQI scales
 - o Symptoms and feelings: Sum of scores of Questions 1 and 2
 - o Daily activities: Sum of scores of Questions 3 and 4
 - o Leisure: Sum of scores of Questions 5 and 6
 - o Work and school: Score of Question 7
 - o Personal relationships: Sum of scores of Questions 8 and 9
 - o Treatment: Score of Question 10.

NOTES:

1. If any question associated with a scale is unanswered the corresponding scale is not calculated.
 2. If 2 or more response options are ticked, the highest score is recorded.
 3. In case of a response between 2 tick boxes, the lower score is recorded.
- Serious Adverse Events (SAEs)
 - SAEs are coded by AbbVie using the Medical Dictionary for Regulatory Activities (MedDRA). One or more Preferred Terms (PT) are associated with each SAE. These terms will be provided to DICE who will map them to the corresponding System Organ Class (SOC).
 - Study-emergent SAE: An SAE is considered study-emergent if its onset date is on or after the date of informed consent and at most 70 days after the date of last administration of adalimumab.
 - Relation of SAE with study medication:
 - o Related: Probably related, possibly related, probably not related, unknown, not reported, missing.
 - o Not related: Not related.
 - Non-Serious Adverse Events (AE)
The CRF allowed the reporting of non-serious adverse events. These events are coded using MedDRA Version 20.0.
 - AS/PsA treatments recorded at baseline and during the study are coded using the World Health Organization (WHO) Drug Dictionary, Version 1 December 2011.

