6.0 Investigational Plan

6.1 Selection of Study Population

The study population will consist of adult patients with diagnosed AS / PSA in whom adalimumab treatment will be initiated. All medications will be prescribed in the usual manner in accordance with the terms of the marketing authorization and in line with the Belgian reimbursement criteria.

The patients must provide written informed consent prior to study participation and must give written authorization to the investigator to use and/or disclose personal and/or health data before entry into this observational study.

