1.8 Patient Population

The following analysis sets are considered for the analysis:

Intention to Treat (ITT) Set: All patients enrolled in the study, who received at least one dose of adalimumab, and for whom any follow-up data are available.

Per Protocol Set (PPS): All patients of the ITT Set without any major protocol deviations. Protocol deviations will be reviewed and classified as minor or major during a data review that will be held before database lock.

Safety Set: All patients enrolled in the study, who received at least one dose of adalimumab, and for whom any follow-up data are available.

All baseline and efficacy data will be analysed on the basis of the PPS. In case the difference between the ITT Set and PPS exceeds 10% of the patients of the PPS, the TWPI data will also be analysed for the ITT Set.

The analysis of adverse events and of the course of the study will be performed on the basis of the Safety Set.

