1.9 Data Handling

The following data handling transformations are performed for the analysis:

Onset data

- Date of enrolment is taken to be date of informed consent

WPAI Questionnaire

- For patients with (number of hours missed due to psoriasis = number of hours worked = 0), Absenteeism, Presenteeism and Total work productivity impairment are set to missing.
- If the answer to Question 1 of the WPAI Questionnaire is not YES but there is an answer to any of Questions 2, 3, 4, or 5, then the answers to these questions are considered to be missing.

Serious Adverse Events

In case of a partial or missing date for the start of a serious adverse event it will be

assumed that the event was study-emergent unless it can be determined from the partial start or stop date that the event definitely started before the date of informed consent or more than 70 days after the last administration of study medication.

Last Observation and Last Attended Visit

The analysis of individual scales is performed for each visit and for the last observation after baseline. For multi-item questionnaires the last observation after baseline is defined as the observation for the last visit after baseline at which any of the items of the questionnaire is completed.

The analysis of the relation between variables is performed for data recorded at baseline, at Month 18, and at the last attended visit.

Other Missing Data

No other estimation will be performed of missing data. In order to obtain estimates for the end of the study, use is made of the last observation after baseline. If date of completion/withdrawal was missing it has been set to date of last contact.

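### Study-emergent SAEs are counted from informed consent with no split at first dose, so a pre-dose SAE could be pooled with on-drug events and labelled related to adalimumab

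*SAP*

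**What the plan says.** **Window.** SAP 1.6 sets the start: "An SAE is considered study-emergent if its onset date is on or after the date of informed consent". It sets the end at "at most 70 days after the date of last administration of adalimumab". The end is tied to the drug and the start is not.

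**Incomplete dates.** Under SAP 1.9, an SAE with a partial or missing start date is "assumed that the event was study-emergent unless it can be determined from the partial start or stop date" that it began before consent or more than 70 days after the last dose. First dose plays no part.

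**Causality.** SAP 1.6 groups the assessments as "Related: Probably related, possibly related, probably not related, unknown, not reported, missing". Only *not related* falls outside that group. The options listed in SAP 1.5 are "Causality with adalimumab (probable, possible, probably not related, not related, not assessable"; the last of these is not named in the grouping.

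**Who is counted.** SAP 1.8 reads: "Safety Set: All patients enrolled in the study, who received at least one dose of adalimumab, and for whom any follow-up data are available". This selects patients and places no limit on when an event began.

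**Where it is used.** SAP 6.1 tabulates study-emergent SAEs overall, by SOC and PT, by maximal severity and by strongest relationship. Its separate list of SAEs that are not study-emergent would not contain an event between consent and first dose.

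**The concern.** A table of SAEs by relationship to a drug is read as describing events in people who had received that drug. Protocol 6.1 describes "adult patients with diagnosed AS / PSA in whom adalimumab treatment will be initiated", with written consent before participation, so consent may precede the first dose. An SAE in that interval cannot have been caused by adalimumab. Under the SAP it would still be pooled with on-drug SAEs, and in some cases it would appear in the related column.

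What is at stake is how clearly the safety description can be read. One impossible attribution in a small SAE table is visible and awkward to explain. The work productivity endpoints are not touched.

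**Working it through.** The plan gives no figure to reproduce, so the check is one of logic.

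**Step 1: can a pre-dose SAE reach the tables?** Write C for the consent date, D for the adalimumab start, L for the last dose and S for SAE onset, in days with C = 0. Take L = 500 as an assumption, so that L + 70 = 570. Compare three rules:

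- SAP 1.6: C ≤ S ≤ L + 70
- first dose only: D ≤ S ≤ L + 70
- later of the two: max(C, D) ≤ S ≤ L + 70

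The values of D and S below are assumed, to show how the rules behave.

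| D | S | SAP rule | First dose only | Later of the two |
|---|---|---|---|---|
| 0 | 3 | counted | counted | counted |
| 14 | 3 | counted | not counted | not counted |
| 14 | 10 | counted | not counted | not counted |
| 14 | 20 | counted | counted | counted |
| 28 | 20 | counted | not counted | not counted |
| −14 | −7 | not counted | counted | not counted |
| −14 | 3 | counted | counted | counted |

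When the first dose falls on the day of consent, the rules agree. When it comes later, the SAP rule counts every SAE in between, provided the patient is later dosed and has follow-up data. Patients never dosed are outside the Safety Set. Protocol 6.1.2 excludes previous biologic treatment, so earlier adalimumab exposure is not an alternative explanation.

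**Step 2: can that SAE be labelled related?** SAP 1.6 names seven causality categories, and six map to related: probably, possibly, probably not, unknown, not reported and missing. The mapping does not look at onset relative to first dose. A pre-dose SAE assessed as *not related* stays not related; one in any of the other six categories is counted as related.

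**Step 3: are the data there to separate them?** Yes. SAP 1.5 collects SAE onset and, separately from the consent date, "Start date adalimumab therapy". SAP 1.6 already uses the start date to compute treatment duration.

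**Step 4: how many events?** This cannot be computed. The documents give no distribution of D − C and no SAE rate. For scale only, one affected patient among the planned 200 would be 1/200 = 0.5%; the Safety Set may be smaller than 200.

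**The case against.** The strongest defence is that the SAP does what its label says. The term is study-emergent, not treatment-emergent, and its start matches Protocol 7.4, which collects SAEs from consent or authorization. A reader might infer that the SAP contradicts the protocol or misdefines an exposure window; the documents support neither. What remains is that a collection period is being used, without a split, in a table about drug relationship. SAP 1.10 says the safety analysis was added at the SAP stage, so the protocol did not prescribe that table.

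The interval may also be empty. Protocol 6.1.1 requires patients newly initiated on adalimumab, SAP 1.3 describes initiation in the past tense, and Appendix G allows screening and baseline at one visit. This stands, and it is why no size can be claimed. A reader might assume a gap of 2 to 8 weeks and compare it with 18 months (18 × 365.25/12 ≈ 548 days): 14/562 = 2.5% to 56/604 = 9.3% of the time, or 14/632 = 2.2% to 56/674 = 8.3% with the 70-day tail. No document supports that gap. The tables are also patient frequencies, so a share of time is not a share of SAEs.

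Investigators can mark a pre-dose event *not related*, and Protocol 7.3 has them give another cause when they see no reasonable possibility of a relationship. That will often settle the matter. The default acts only on the remaining assessments, and for on-drug events it is a defensible cautious choice. It would be too strong to say that all pre-dose SAEs become related.

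A reader might also infer that a false related count goes to ClinicalTrials.gov. In SAP 6.1 the footnote marks the overall and the SOC/PT tables, not the relationship table. The marked tables would pool pre-dose events but carry no relationship label.

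Finally, the by-patient lists partly mitigate the problem, since onset and start dates are both recorded.

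**Conclusion.** The point holds as a minor one. On the text of SAP 1.6, 1.8, 1.9 and 6.1, an SAE after consent and before first dose is pooled with on-drug SAEs. If its causality is probably not related, unknown, not reported or missing, it is counted as related to adalimumab. An effect on the related count needs four things together: a real gap, an SAE within it, later dosing with follow-up data, and a causality entry other than *not related*. The number of such events is unknown and may be zero. The study is descriptive, and safety is not among its objectives or endpoints.

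Opening the window at first dose alone may look like the obvious correction, but the documents do not support it. Protocol 7.4 does not require collection before consent. For a patient who started adalimumab first, that rule would tabulate pre-consent SAEs that are captured only incompletely (the row with D = −14 and S = −7).

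**What to change.** 1. Keep SAE collection from consent, as in Protocol 7.4.
2. In SAP 1.6, define the tabulated SAEs as those with onset on or after the later of informed consent and adalimumab start, up to 70 days after the last administration.
3. In SAP 6.1, list SAEs from consent to the day before first dose separately. Leave them out of the relationship table and the default to related.
4. List any recorded on-drug SAEs that began before consent separately, noting that their capture is incomplete.
5. In SAP 1.9, use the same start for partial or missing dates: assume the event falls in the window unless the available dates show that it began before the later of the two dates, or after the 70-day limit.
6. While editing the causality grouping, assign *not assessable* to a group.

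The cost is SAP wording and one date comparison per SAE, with no new data. The downside is that tabulated SAE counts may fall slightly; the events removed remain visible in the lists. If every first dose was given on or before the day of consent, the tabulated counts do not change.
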